4 REGISTRATION PROCEDURES

4.1 REGISTRATION PROCESS

To register a subject, the following documents should be completed by the research coordinator and signed by [name], PhD.:

- Signed Eligibility Screening Worksheet
- Registration Form

[name] will then verify eligibility. To complete the registration process, [name] will:

- Assign a subject trial number
- Register the subject on the trial
- Start the infusion of UTX as per the protocol

After the first two (2) subjects are enrolled and completed infusion with trial drug (UTX) or after the first six months, whichever is first, the DSMB will meet to review safety. No further subjects may be enrolled into the trial until the DSMB has reviewed the study data and submitted their conclusion to the Sponsor and IRB. The DSMB will inform the Sponsor that the study may proceed as follows, to reduce the dose, or to terminate the study due to safety concerns as noted below.

DSMB Permits the Trial to Continue

If the DSMB permits the study to continue, an additional three (3) subjects will be enrolled and infused with trial drug (UTX). Upon completion of the infusion of trial drug into these additional subjects, the DSMB will meet again to review the safety data from these three subjects and the cumulative safety from this trial. The DSMB will inform the Sponsor of any safety concerns.

DSMB Terminates Trial

The Sponsor ([name]) may challenge this decision as per the DSMB charter. However, no subject may be enrolled into the trial during the challenge.

5 TREATMENT PLAN

5.1 AGENT ADMINISTRATION

Given the severity and the consequences of relapse in NMO, use of an active treatment is considered mandatory. The potential of currently utilized drugs and techniques to reduce the inflammation in NMO has been established primarily through expert consensus and small open label and retrospective studies.

Treatment will be administered in an inpatient hospital setting and absolute neutrophil count must be $> 1000/\mu\text{L}$ and platelet count must be $> 50,000/\mu\text{L}$ before infusing UTX.

Guidelines for Administration of Ublituximab

- *Method of Administration:* ublituximab will be administered as an intravenous infusion.
- *Potential Drug Interactions:* No drug interactions have been reported to date.
 - *Pre-medications:* All subjects receiving an infusion of UTX must be pre-medicated approximately 30 minutes prior to the dose of ublituximab with an antihistamine (diphenhydramine 25 - 50 mg or equivalent) and oral acetaminophen 650 mg (or equivalent).

NMO/NMOSD subjects will be given an infusion of 450 mg/day of UTX over four (4) hours consecutively on the first day while at the Johns Hopkins Hospital.

5.2 GENERAL CONCOMITANT MEDICATION AND SUPPORTIVE CARE GUIDELINES

No investigational or commercial agents or therapies other than those described below may be administered with the intent to treat the subject's acute NMO relapse.

No steroids may be administered outside of protocol requirements for acute treatment as outlined.

Infusion Reactions with ublituximab: Infusion related reactions have been frequently reported with ublituximab. All subjects treated with ublituximab require pre-medication approximately 30 minutes prior to the dose of ublituximab with an antihistamine (diphenhydramine 25 - 50 mg or equivalent) and oral acetaminophen 650 mg. Symptomatic infusion reactions, despite pre-medication, may be treated at the discretion of the treating physician, including but not limited to: additional antihistamines, oxygen and bronchodilators.

Symptomatic treatment for neuropathic or muscular pain and muscle spasms may be treated using concomitant medication as per standard of care.

5.3 DURATION OF THERAPY

In the absence of treatment delays due to adverse event(s), treatment will begin on Day 1 with UTX and with steroids on day 1 and continue to day 5, unless one of the following criteria applies:

- Delay in transfer to the Johns Hopkins Hospital from an outside institution. In the event that an NMO patient interested in participating in the trial presents with an acute relapse to outside institution, there should be no delay in beginning treatment with standard of care steroid therapy. The subject may enroll in this trial and receive one dose of ublituximab on the first day of hospitalization at the Johns Hopkins Hospital if the transfer takes place within 5 days of presentation. Steroid treatment will continue at Johns Hopkins to ensure a total of 5 days of steroids.

- Intercurrent illness that prevents administration of treatment,
- Unacceptable adverse event(s) during the infusion of steroids or UTX,
- Subject decides to withdraw from the trial, or
- General or specific changes in the subject's condition render the subject unacceptable for further treatment in the judgment of the investigator.

The reason for trial removal and the date the subject was removed must be documented in the Case Report Form. Subjects who discontinue therapy due to an adverse event will be followed until resolution or stabilization of the adverse event.

5.4 DURATION OF FOLLOW UP

After discharge from the hospital, subjects will be followed as an outpatient clinically at days 90 and 180. In addition, subjects will be monitored monthly for B cell counts for as long as it takes for B cells to replete to a minimum of 0.5% for patients who will continue to be treated with B-cell depleting agents for preventive care, according to standard of care, or to a minimum of 5% for patients who will use other preventive strategies. For most subjects, the duration of B-cell depletion with UTX is up to 9 months. Subjects removed from the trial for unacceptable adverse event(s) will be followed until resolution or stabilization of the adverse event. In addition, subjects will be checked by complete blood count with differential and complete metabolic profile for evidence of toxicity to other cells (e.g., neutrophils) or organs such as kidney or liver function.

6 DOSING DELAYS/DOSE MODIFICATION

A single dose of 450 mg of ublituximab will be administered under the direction of the Principal Investigator, [name] while the subject is in the hospital. It is required that the absolute neutrophil count be $\geq 1000/\mu\text{L}$ and the platelet count be $\geq 50,000 \mu\text{L}$ before the infusion. If the liver enzymes (ALT and/or AST) are > 5 times the upper limit of normal (ULN) of the normal range at the John Hopkins medical laboratory or if the neutrophil count and platelets counts are below acceptable levels as described, the dose of ublituximab will be held for up to 48 hours until the laboratory values return to within acceptable range. If all labs above do not return to within acceptable range within 48 hours, the subject will not receive the ublituximab infusion and will be withdrawn from the study.

7 TRIAL ASSESSMENTS AND TREATMENT

Given the severity and the consequences of a relapse in NMO, use of an active treatment is considered mandatory. The potential of currently utilized drugs and techniques to reduce the inflammation in NMO has been established primarily through expert consensus and small open label and retrospective studies.

This is Phase 1, unblinded safety trial in NMO/NMOSD subjects in which subjects will receive one (1) infusion of 450 mg of intravenous ublituximab at the onset of an NMO exacerbation in addition to standard of care treatment with daily intravenous methylprednisolone at 1000 mg for five days.

The trial phases and durations, as well as standard of care treatment and MRIs are shown in the table below. For those who complete the trial, it is comprised of 4 potential phases: Screen, Steroid Treatment, Plasma Exchange (if necessary) Treatment and Follow-Up.

Table S1: Ublituximab in NMO Trial Phases and Timings of Treatments/MRIs

Phase:	Screening 1 day	Steroid Treatment* 5 days					Plasma Exchange (if necessary)	Follow-up Monthly	Follow-up 90-Day Visit	Follow-up 6 Month Visit
Day	0	1	2	3	4	5	6-20	30, 60, 90, 120, 150, 180, 210, 240, 270	90	180
Treatment		T ^{1,2}	T ¹	T ¹	T ¹	T ¹				
Exam/Lab	E/L	E/L	L	L	L	E/L	E/L	L	E	E
MRI of affected area	M					M	M		M*	

T1: Administration of methylprednisolone 1000 mg intravenously
T2: Administration of 450 mg of ublituximab intravenously
E: Neurological examination
L: Lab testing
M: MRI, as indicated by standard of care; M*: MRI for research purposes

Screening Phase

The purpose of the Screening Phase is to assess subject eligibility. This process includes an MRI scan (standard of care) to identify a contrast enhancing lesion(s) in the optic nerve and/or spinal cord.

Subjects must have circulating B cells to enroll in the trial and receive ublituximab therapy. For those who have not received B cell depleting medications in the past 12 months (rituximab, ofatumumab, ocrelizumab, ublituximab), a normal B cell count of 5-20% of total lymphocytes must be present in the circulation, confirmed by a limited flow cytometry panel of CD3, CD4, CD19 and CD20. For those who have received a B cell depleting medication in the past 12 months, a minimum of 0.5% of total lymphocytes must be B cells. The working hypothesis is that when a subject has an acute attack following preventive therapy with B cell depleting agents, the remaining or returning B-cells are very aggressive and may catalyze the attack.

Steroid Treatment Phase

High dose (1000 mg) intravenous methylprednisolone will be given to all subjects with MRI-confirmed active lesions at onset of the attack according to standard of care. During the first day of steroid treatment or as early as possible in the steroid treatment course, 450 mg of intravenous ublituximab will be administered to all subjects.

Effort will be focused on giving the ublituximab as early in the steroid treatment process as possible. If a subject's admission or transfer to the Johns Hopkins Hospital is delayed, standard of care therapy with steroids will begin as soon as possible. The subject may enroll in this trial and receive ublituximab on the first day of hospitalization at the Johns Hopkins Hospital if the transfer takes place within the Steroid Treatment Phase.

Prior to the infusion, a complete cell count with differential and complete metabolic panel screening for abnormalities in neutrophil count, platelet count and liver enzymes.

All subjects who fail to clinically respond by day 5 will be recommended for plasma exchange as per standard of care. A beneficial response is generally considered an improvement in the specific deficit(s) that led to the hospitalization. Depending on those specific deficits, the criteria that are routinely used at Johns Hopkins to indicate treatment response(s) in motor, sensory, autonomic and visual function are:

1. An improvement in strength by the Motor Research Council strength scale by at least 1 full point in at least two isolated muscles of at least one limb, or
2. An increase of two Rydel tuning fork units in at least one affected limb.
3. Improvement in bowel and/or bladder function from incontinence to at least partial voluntary control.
4. An improvement in visual acuity using bedside Snellen chart of ≥ 2 lines.

If subjects do not require escalation to plasma exchange because they fulfill the clinical criteria above, an MRI may be performed to confirm resolution of the inflammatory lesion, according to standard of care at Johns Hopkins. Based on the MRI and other clinical factors, the treating physician may proceed to discharge the subject home or change the plan to escalate immunosuppression to plasma exchange for continued treatment of the acute exacerbation.

Findings by MRI that may influence escalation to plasma exchange typically include extension of enhancement, involvement of new areas of the nervous system or an increase in the area of T2 hyperintensity. Historically among the NMO/NMOSD subjects treated at Johns Hopkins, approximately 50% of NMO/NMOSD subjects improve from a relapse with steroids alone. The other 50% require escalated care with plasma exchange.

Before discharge from the hospital, the subject will be scheduled for follow up in the NMO Clinic in 90 and 180 day visits. In addition, subjects will be sent to a local lab for monthly CD19 monitoring until the B cell counts replete to a minimum of 0.5% for patients who will continue to be treated with B-cell depleting agents for preventive care, according to standard of care, or to a minimum of 5% for patients who will use other preventive strategies. These results will be reviewed by the PI, [name].

Plasma Exchange Treatment Phase

Should subjects not meet above clinical criteria to be discharged home, escalation to treatment with plasma exchange is standard of care.

The plasma exchange treatment phase begins at the end of the Steroid Treatment Phase and will last up to 14 days. During the Plasma Exchange Treatment Phase, subjects will undergo 1.0 – 1.5 volumes of plasma exchange every other day according to standard of care. At the end of this phase, a second MRI may be performed to confirm resolution of the lesion, according to standard of care. If any further acute immunosuppressive treatment for the acute NMO flare is required and provided according to standard of care, the subject will continue to be followed for safety issues, but the clinical efficacy data will not be included in the statistical analysis. Historically among NMO/NMOSD

subjects treated at the Johns Hopkins Hospital, approximately 95% of NMO/NMOSD subjects who complete plasma exchange are discharged following completion of the plasma exchange.

Follow-up

The primary outcome is safety for the duration of the period of B cell depletion. Secondary efficacy outcomes will be assessed at follow up 90 and 180 days after initial hospitalization for the acute relapse. In addition to a thorough history and physical examination, including EDSS rating, visual examination and timed walk, a research MRI of the spine will be performed at day 90 to compare to the relapse lesion. In addition, subjects will be sent to a local lab for monthly CD19 monitoring until the B cell counts replete to a minimum of 0.5% for patients who will continue to be treated with B-cell depleting agents for preventive care, according to standard of care, or to a minimum of 5% for patients who will use other preventive strategies. These results will be reviewed by the PI, [name].

Withdrawal

For subjects who discontinue or withdraw from the trial, investigators will continue to monitor subjects who have ongoing neurologic deficits while the subject remains in the hospital. This involves periodic neurologic exams and close observation in collaboration with the treating physician.

Subjects unable to tolerate ublituximab will be withdrawn from the trial. A tolerability issue for the purpose of withdrawing to alternative treatment is defined as a moderate or severe side-effect or complication related to treatment, which is unacceptable to the subject; or a clinically significant change in hematologic, hepatic, or renal laboratory parameters that, in the opinion of the investigator, would require a change in treatment.

Definition of Completer and Maximum Duration of Participation

A completer is defined as a subject who has completed all of the clinically necessary phases of the trial, as per standard of care, and has followed up in the NMO Clinic for all follow up visits. The maximum duration of participation is up to 9 months for most subjects.

Magnetic Resonance Imaging in the Trial

The trial will utilize MRI for spine imaging with and without contrast during the trial for relapses, as per standard of care and for research purposes on 90-day follow-up. In cases of poor creatinine clearance, contrast will not be used. According to standard of care, MRI scans in the trial will be performed at the initiation of the relapse. On follow up, the MRI is a research procedure. For purposes of this trial, standard of care MRIs of the spine will be reviewed by trial staff; the following characteristics will be recorded for research purposes:

1. Length of sagittal spine T2 lesion in centimeters in all subjects who obtain MRIs, and
2. Length of sagittal spine T1-post contrast lesion in centimeters and/or orbital T1-post contrast lesion in millimeters in those subjects who additionally receive gadolinium contrast.

A single blinded Independent Reader will review the MRI for research purposes. The reader will be blinded to the treatment assignments and time sequences of the scans.

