9 TRIAL CALENDAR/EVALUTION TABLE

Table 6: Schedule of Events

Phase:	Screen (1 day)	Steroid Treatment (5 days)					Plasma Exchange (if necessary)	Follow up		
		1	2	3	4	5		Monthly	90 day	6 month
Day	0	1	2	3	4	5	6-20	30, 60, 90, 120, 150, 180, 210, 240, 270	90	180
MRI of the affected area (brain, c/t spine)	M					M	M		M	
Administration of treatment		Steroids on days 1-5 UTX: 1 dose on day 1 or as early as possible in this phase								
Informed Consent	X									
Eligibility	X									
Demographic, NMO and Medical History	X								X	X
Prior NMO treatments	X									
Vital signs, weight	X	X	X	X	X	X			X	X
Neurological Exam	X	X	X	X	X	X			X	X
Laboratory assessment	X	X	X	X	X			X		X
HCVA		X			X	X			X	X
EDSS		X			X	X			X	X
Timed 25-Foot Walk		X			X	X			X	X
Adverse Events		X	X	X	X	X			X	X
Concomitant Meds	X	X	X	X	X	X				

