Timed 25-foot walking trials will be assessed on days 1 and 5 during the steroid phase and weekly in the plasma exchange phase. The Timed 25-Foot Walk test is a quantitative measure of lower extremity function. If required, the subject may use an appropriate assistive device to walk as quickly as he/she can from one end to the other end of a clearly marked, unobstructed, 25-foot course. Every effort will be made to use the same testing hallway for every Timed 25-Foot Walk test. Potential for external distractions should be kept to a minimum as much as possible. A subject will stand with the toes of his/her shoes on the starting line (identified by a taped mark on the floor) and timing will begin when any part of the subject's foot crosses the tape. Timing will end when any part of the subject's foot crosses the finish line (identified by a taped mark on the floor). Time will be recorded in seconds and rounded to the nearest tenth of a second using a stopwatch provided for this trial. The task is immediately administered again by having the subject walk back the same distance. The average of the two values will be recorded in the case report form.

Objective Efficacy Endpoints

MRIs will be performed for standard of care and research purposes and will be used to make clinical decisions about escalation of immunosuppressive treatment. For this trial, the MRIs will also be analyzed for two parameters: length and T2 hyperintensity in the spinal cord and optic nerve and length of T1 post-contrast enhancement if available.

Number of days in the hospital and requirement for plasma exchange will also be recorded on the CRFs.

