11.2 GENERAL ANALYSIS CONVENTION

Interim Analysis

There will be no interim analysis.

Statistical Analysis

A summary of the number and percentage of subjects with any adverse event, any serious adverse event, adverse events leading to permanent discontinuation of trial drug, and trial drug-related adverse events will be reported.

Change in neurologic outcomes on the EDSS, Timed 25-Foot Walk and HCVA scales from admission to discharge will be analyzed by paired t-tests with significant p-values considered less than 0.05.

By MRI, length of T2 hyperintensity and length of T1-post contrast enhancement should be stable or reduced by discharge. A paired t-test will be used to compare changes in these values with significance considered at p-values less than 0.05.

Continuous data will be described using the following descriptive statistics: n, mean, median, minimum and maximum. Data will be displayed in all listings sorted by subject number.

When count data are presented, the percentage will be suppressed when the count is zero in order to draw attention to the non-zero counts. A row denoted "Missing" will be included in count tabulations where necessary to account for dropouts and missing values. Unless otherwise specified, the denominator for percentages will be the number of subjects with a non-missing assessment within the analysis population of interest.

SAS Version 9.2 will be used to perform all analyses.

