11.9 EFFICACY ANALYSES

Secondary endpoints of clinical outcomes will be monitored for efficacy using three functional neurologic tests, the Expanded Disability Status Scale (EDSS), Timed 25-Foot Walk and High Contrast Visual Acuity (HCVA). These will be assessed days 1 and 5 of hospitalization and weekly thereafter for the first three weeks (Days 13 and 20, if needed). The primary analysis will be a change from baseline to Day 90 and the secondary analyses will be a change from baseline to Days 5, 20, and 6 months.

For this secondary efficacy endpoint, the MRIs will be analyzed for two parameters: length of T2 hyperintensity in the spinal cord and optic nerve and length of T1 post-contrast enhancement if available. The secondary analyses for MRI will be a change from baseline to discharge on Day 5 or 20, as well as a change from baseline to follow up at day 90.

Number of days in the hospital and requirement for plasma exchange will be assessed using descriptive statistics.

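### The test of MRI lesion length at discharge uses scans that the protocol makes optional in some places and unconditional in others, and the clinical course decides when the value is taken

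*Combined protocol and SAP*

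**What the plan says.** **The analysis.** Section 11.2 sets an expectation, "By MRI, length of T2 hyperintensity and length of T1-post contrast enhancement should be stable or reduced by discharge", and a test, "A paired t-test will be used to compare changes in these values with significance considered at p-values less than 0.05". The synopsis (Statistical issues) says the same. Section 11.9 fixes the time point: "The secondary analyses for MRI will be a change from baseline to discharge on Day 5 or 20". It also plans a second comparison, with the MRI at the Day 90 follow-up.

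**The scans.** In section 7, a subject who meets the response criteria comes under this sentence: "an MRI may be performed to confirm resolution of the inflammatory lesion, according to standard of care at Johns Hopkins". A subject who goes through plasma exchange comes under this one: "a second MRI may be performed to confirm resolution of the lesion, according to standard of care". The synopsis and section 1.4 are equally permissive. The key to Table S1 reads "M: MRI, as indicated by standard of care; M*: MRI for research purposes", and only the Day 90 scan carries the star. Table 6 in section 9 differs. Its row beginning "MRI of the affected area (brain, c/t spine" has the same mark at screening, Day 5, Days 6-20 and Day 90, with no condition attached.

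**The use of the scans.** Section 10 says that the MRIs "will be used to make clinical decisions about escalation of immunosuppressive treatment". Section 7 names longer enhancement, newly involved areas and a larger T2 area as findings that may lead to plasma exchange.

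**What is recorded.** Under section 7, T2 length is recorded for subjects who have a scan, and post-contrast length only for those who also receive contrast. Section 7 states the Day 90 research MRI of the spine as definite.

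**The concern.** A paired test of change to discharge needs a discharge scan in each subject, taken at a time that does not depend on the result. The protocol secures neither.

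Whether a value exists depends on whether a care-driven scan was done. When it is taken depends on whether the subject was escalated, and the MRI itself can influence that decision. A mean change over whoever was scanned, on whichever day, is hard to interpret as an effect of treatment. A report that lesions had not lengthened by discharge could partly reflect the rule for when discharge is declared.

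**Working it through.** **1. Where the plan stands on the discharge scan**

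| Place | Day 5 scan | Days 6-20 scan | Day 90 scan |
|---|---|---|---|
| Section 7 prose (also synopsis, section 1.4) | permitted, for responders | permitted, after plasma exchange | section 7 and synopsis: will be done, spine |
| Table S1 key | per standard of care | per standard of care | research |
| Table 6 | marked, no condition | marked, no condition | marked, no condition |
| Sections 11.2 and 11.9 | treated as available | treated as available | treated as available |

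The first and third rows conflict for Day 5 and Days 6-20. Section 11.2 has a percentage denominator and a row for missing counts, but no rule for a missing scan in the t-test.

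**2. How the clinical course fixes the value**

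- Responder, Day 5 scan stable or better: discharged, and Day 5 is the discharge value.
- Responder, Day 5 scan worse: may be escalated. Day 5 is then no longer the discharge value, which comes from a later scan if one is done.
- Non-responder: recommended for plasma exchange. The discharge value is the optional scan after it.

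Unfavourable Day 5 values can thus be replaced by later ones, even if everyone is scanned. Section 7 gives a historical escalation share of about 50%, so 5 × 0.5 = 2.5 subjects would take the later route if that share, observed on steroids alone, applied here.

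**3. Number of pairs**

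The plan gives no power, SD or scan rate for MRI, so there is no calculation to reproduce. Section 11.1 gives 5 subjects and 4 expected completers: 5 − 1 dropout = 4, provided the one screen failure is outside the five (5 − 1 − 1 = 3 if inside).

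For n pairs, a two-sided test (sidedness is not stated, so this is assumed) needs an observed |mean|/SD above t(0.975, n−1)/√n:

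| Pairs | Critical t | Needed mean/SD | Power at a true standardised change of 1.0 |
|---|---|---|---|
| 5 | 2.776 | 1.24 | 40% |
| 4 | 3.182 | 1.59 | 29% |
| 3 | 4.303 | 2.48 | 18% |
| 2 | 12.706 | 8.98 | 9% |

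If each of 5 subjects is scanned with assumed probability s, then P(at most 1 pair) = (1−s)^5 + 5s(1−s)^4 and P(all 5) = s^5:

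| s | Expected pairs | At most 1 pair (no test possible) | All 5 |
|---|---|---|---|
| 40% | 2.0 | 34% | 1% |
| 50% | 2.5 | 19% | 3% |
| 60% | 3.0 | 9% | 8% |
| 80% | 4.0 | 1% | 33% |
| 100% | 5.0 | 0% | 100% |

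**4. Selection by branch**

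Take the 50/50 split and assume scan rates of 80% in non-escalated and 40% in escalated subjects. The non-escalated share of those scanned is 0.5×0.8 / (0.5×0.8 + 0.5×0.4) = 0.40/0.60 = 0.667. The mean shifts by 0.667 − 0.5 = 0.167 of the gap between branches. Reversing the rates reverses the shift, and equal rates give none.

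In 200,000 simulated trials with a true overall mean change of zero, rejection among computable tests was 5.5-5.6% at these rates or their reverse (branch gap 1 SD) and 7.3-7.4% (gap 2 SD). Full scanning gave 5.1% and 5.6%. At 100% against 50% it was 5.6% and 7.9%. The harm lies more in the estimate and the lost pairs than in the error rate.

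**The case against.** The strongest reply is that the discharge scan is foreseen for everyone. Table 6 marks it without condition. The section 10 sentence on escalation opens by saying that MRIs will be done for both care and research. The prose provides a scan in each branch. If all five are scanned, no subset arises.

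This defeats several stronger readings that a reader might infer:

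- *That Day 90 is the only scan scheduled for every subject.* Table 6 marks Day 5 in the same way, and the admission MRI is part of screening.
- *That subjects who recover go unscanned.* Section 7 attaches the Day 5 scan to responders.
- *That the large critical t values show selection.* They show small n. Even with five pairs, power is 40% at a standardised change of 1.0.
- *That post-contrast values will be scarce.* They cannot outnumber the T2 values, but no rate of withheld contrast is given, and screening looks for an enhancing lesion.

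It may also be said that section 11 defers data handling to a later SAP, that section 11.1 relies on summary statistics, and that no decision depends on this test. That limits the weight of the point. It does not remove it: the test and the expected direction are already written into the protocol, no text says which statement about the scans governs, and the dependence of the discharge day on the clinical course remains with complete scanning.

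**Conclusion.** The point holds, as a change that should be made rather than one on which the trial depends. Two parts rest on the text alone: the passages conflict on whether the discharge scans are required, and the time of the discharge value depends on a course that MRI findings can alter.

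A selected subset is likely, not established. The documents do not support saying that the test will use one, or that missing scans favour the drug. The sizes above rest on assumed scan rates, an assumed gap between branches and a two-sided test. The endpoint is secondary, in a five-subject safety trial, and the Day 90 comparison does not rest on the optional scans.

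**What to change.** 1. In sections 11.2 and 11.9 and the synopsis, make change from baseline to the Day 90 research MRI the MRI comparison for cord lesions.
2. Report discharge scans descriptively, one line per subject: day, escalated or not, reason for the scan, and lengths. State the number scanned in each branch. Drop the t-test and the group statement that lesions should not have lengthened by discharge.
3. Reconcile section 7, the Table S1 key and Table 6 on whether the Day 5 and Days 6-20 scans are required. Add no scans for this purpose.

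The cost is wording only, with three losses. There is no tested group MRI result at discharge. Subjects with optic neuritis alone have no tested MRI change, because the Day 90 scan is described as of the spine, so their orbital measurements are only listed. The Day 90 scan may also be missing for the one dropout expected in section 11.1, which would leave 5 − 1 = 4 pairs at most.
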